1.0 Introduction

1.1. Statement

The study will be conducted according to US and international standards of Good Clinical Practice (FDA Title 21 part 312) and International Conference on Harmonization guidelines, applicable government regulations and institutional (Mayo Clinic) research policies and procedures.

1.2 Definitions

Term	Description
YE560	YELLOW 560 fluorescence module (available for KINEVO 900)
CIP	Clinical Investigation Plan
CRF	Case Report Form
AEF	Adverse Event Form
Device Manufacturer	Carl-Zeiss Meditec AG (Jena, Germany)
FDA	Food and Drug Administration
IDE	Investigational Device Exemption
IRB	Institutional Review Board
OR	Operating Room
Sponsor	Carl Zeiss Meditec, Inc. (Dublin, CA)
VS	Vestibular Schwannoma
GTR	Gross Total Resection
HNP	Head and Neck Paraganglioma
HNS	Head and Neck Schwannoma

1.3. Purpose

The purpose of this study is:

- To evaluate the benefit of using intravenous fluorescein sodium (FS) and YELLOW 560 nm microscope filter (YE560) during surgery for vestibular schwannomas (VS) menioma, head and neck paraganglioma (HNP), or head and neck schwannoma (HNS)
- To determine the optimum FS dose and timing to be used with the YE560 device

VSs are benign, slow-growing neoplasms of the myelin-containing Schwann cells of the vestibular division of the vestibulocochlear nerve. These tumors are in close proximity to the facial nerve and cochlear division of the vestibulocochlear nerve. These nerves allow for facial movement and hearing, respectively. Management of these indolent tumors has shifted to more conservative means of minimizing growth and maintaining facial function and hearing. Management of VSs includes observation with serial MRI exams, stereotactic radiosurgery, and microsurgery.

Similarly, HNP, HNS and skull base meningiomas are benign but infiltrative tumors that grow adjacent to important neurovascular structures including, the cranial nerves. These tumors can be observed, treated with radiosurgery, or microsurgery based on size, symptoms, and patient preference.

When microsurgical resection of VS, schwannomas, meningiomas, or paragangliomas is performed, distinguishing the tumor from healthy nerve tissue is performed via direct visualization under light microscopy and tissue manipulation. Often, these tumors are intimately associated with the surrounding nerves, and can be difficult to distinguish under the microscope. In many cases intraoperative cranial nerve monitoring allow for the use of a stimulation probe to help make this distinction.

The hypothesis is that FS and YE560 may be used as a supplementary visualization aid to better distinguish the tumor from healthy nerve tissue and secondarily improve conservation of facial and hearing nerve function and attainment of gross total resection (GTR). Use of intravenous FS has FDA approval for ophthalmologic applications and its safety profile is well documented (Yanuzzi 1986). There have been studies demonstrating uptake of FS by VS tissue in vitro (Perez 2018). Additionally, the feasibility and utility of intraoperative fluorescence from FS intravenous administration and use of YE560 have been demonstrated with peripheral schwannomas in vivo (Pedro 2019). The YE560 fluorescence module available for the KINEVO 900 will be used to visualize fluorescein-stained tissue in yellow light. FS will be administered upon initial visualization of the VS. Utility of FS and YE560 will be assessed via surgeon survey, correlation with biopsy of fluorescent VS tissue, and color image analysis of healthy and VS tissue using the YE560.

A total of 90 consenting patients, either male or female, clinically indicated for resection of a suspected VS will be enrolled into the study. No exclusions will be made for recurrent VS following stereotactic radiosurgery or microsurgical resection or VS associated with neurofibromatosis type 2 (NF-2).

1.4. Application

The document applies to the YE560 Fluorescence option available for KINEVO 900 supplied for the intended clinical investigation and protocol at the specified hospital site. The Clinical Investigation Plan (CIP; or Sponsor Protocol) must be agreed to by the Sponsor and Clinical Investigators involved in the study.

1.5. Responsibility and Authority

Mayo Clinic Institutional Review Board (IRB) for Human Research must grant approval of the study, and record their determination of the study's risk profile as a non-significant or significant risk medical device study.

Clinical investigators, research collaborators, and Carl Zeiss Meditec, Inc staff involved in the study are responsible for implementing the described procedures.

2. Details of the clinical Investigation

2.2. Institution where investigation will be conducted

Mayo Clinic
Rochester, Minnesota, USA

2.3. Analysis of the Study Data

The Study results will be analyzed by:

- Clinical Investigator at Mayo Clinic (Rochester, MN, USA)

2.5. Database Management

Clinical Investigators shall be responsible for day-to-day database management, keeping a secure record of all patients recruited for the purposes of the study and details of the procedure performed. All data generated from this clinical study will comply with Federal Drug and Food Administration (FDA) compliant guidelines.

2.6. Security of Patient Data

Patients will be assigned unique identifiers codes upon enrollment. Digital images and videos captured from surgery will be saved on a department drive in a folder with limited access. Electronic data will be stored in Rave Electronic Data Capture (Medidata, New York, NY). Digital images, raw procedure data, photos, macroscopic images, video, other imaging data (e.g. MRI, CT), medical history or histopathology data used in publication will not contain any information that identifies individual subjects.

2.7. Verification of Source Data

Digital images that are collected are saved in jpeg format for images and mpeg-2 format for videos as a procedure result, which is associated with a unique session ID number. Images and videos may be exported from the microscope and saved in various common image file formats (e.g. jpg, bmp, tif). Source data can be verified by viewing images in the original saved format (Procedure Result) via the instrument software.

2.8. Data Storage

Data will be collected from surgeon surveys and the medical record and recorded electronically in Rave Electronic Data Capture (Medidata, New York, NY), a product in compliance with FDA 21 CFR Part 11. Only authorized research staff will have access to the electronic data. Paper copies of informed consent forms and completed surgeon surveys will be stored in a binder kept by the study coordinator.

2.9. Data Retention

The principal investigator will retain clinical research data for 3 years after completion and closure of the study.

3. Overview of the clinical Investigation

3.1. Objectives

Primary objective of this initial feasibility study is to evaluate the benefit of using YE560 to visualize fluorescein sodium (FS) during surgery of VS, Meningioma, HNP, or HNS, determined from surgeon assessment.

Secondary objectives are:

- To evaluate the optimum FS dose and timing to be used with the YE560 device as determined by reported performance on surgeon surveys
- Quantify tissue differentiation of fluorescent VS and adjacent nerves using RGB image analysis
- To report clinical outcomes, including GTR rates, postoperative hearing outcomes, and postoperative facial nerve function

3.2. Literature Review and Rationale

In VS cases where intervention is recommended, stereotactic radiosurgery and microsurgical resection offer two therapeutic options. Comparatively, microsurgical resection carries the advantage of offering the highest chance of a cure. The goal of surgery remains to resect the tumor while maintaining the integrity of the adjacent, and sometimes intimately adherent cochlear and facial nerves. Thus, gross total resection cannot always be achieved. Nakatomi and colleagues described the superior 15-year recurrence-free survival rates in patients receiving gross total resection (56%) versus subtotal resection (8%).¹ Intraoperatively, maximum resection of the tumor while preserving facial function and hearing relies on the ability to distinguish normal nerve tissue and tumor. Additional means of distinguishing these tissues could facilitate greater rates of gross total resection and preservation of cranial nerve function.

Intravenous FS has been used in ophthalmologic and neurosurgical applications to differentially cause fluorescence in tissues intraoperatively. This technique was reported in 1948 by Moore et al² and more recently by Koc and Toda in obtaining gross total resection of high grade gliomas^{3,4}. Fluorescein angiography has been routinely used for retinal imaging for vascular conditions and neoplasms since first described in 1961.⁵

As previously mentioned, two recent studies have demonstrated the application of intravenous FS to VSs. Perez et al have reported in vitro preferential uptake of FS in VS cells compared to native Schwann cells.⁶ Additionally, Pedro et al demonstrated feasibility of YE560 and intravenous FS in visualizing benign peripheral nerve sheath tumors—an identical histological entity to VS—located in the extremities.⁷ In our proposed study, the fluorescence light will be visualized with a surgical microscope (Kinevo 900) with YE560 fluorescence module. The device has optimized filter and optics; therefore, the concentration of fluorescein sodium per patient used in this study is expected to be lower than in earlier studies that do not use the fluorescence module.

Intraoperative fluorescence imaging has been utilized in the resection of HNP and meningiomas. Indocyaninegreen fluorescence angiography has been used to assess post-embolization vascularity of paraganglioma to estimate bleeding risk.⁸ FS has been utilized with the YE560 to distinguish meningioma and hyperostosis from surrounding brain and healthy bone.⁹

FS is FDA approved for ophthalmologic applications. The standard dose for retinal imaging in adults is a 500 mg bolus into a peripheral vein (7.1 mg/kg in a 70 kg patient).¹⁰ The safety profile of intravenous FS is well-described in the ophthalmology literature. Nausea and vomiting are the most common side effect reported, but 87% of surveyed ophthalmologists reported rates less than 5%. Urticaria is estimated to occur at a rate of 1 in 82 patients. Severe adverse reactions, including respiratory reactions (1:3,800), cardiac events (1:5300), and tonic-clonic seizure (1:13,900) are rare and estimated to occur cumulatively in 1 in 1900 patients.¹¹

3.4. Hypothesis

12. Given prior evidence of preferential uptake of FS in VS and meningiomas due to disrupted blood brain barrier, we hypothesize that use of intravenous FS will allow for visual differentiation of tumor and surrounding structures and nerves using YE560.
13. The optimal dosing for FS has not been established for this application. Pedro et al utilized 0.5-1.0 mg/kg body weight to visualize peripheral nerve sheath tumors with YE560. The authors found saturation of all tissues with 3-4 mg/kg dose within 18 seconds of administration. The blood-brain barrier may play a modulating role. Schebesch et al (2013) used 3-4 mg/kg to visualize malignant gliomas and observed fluorescence after 20-30 minutes. We suspect that the optimal dose will be 3-4 mg/kg, and peak fluorescence will take a similar amount of time. However, we will initially utilize 1.0 mg/kg SF administered at the time of first visualizing the tumor to enable subsequent doses (up to a maximum of 500 mg or 7 mg/kg). This will allow us

to determine the minimum effective dose and observe the time to peak fluorescence. The optimal dosing strategy will be finalized after the first 10 cases.

14. We hypothesize that the surgeons will be satisfied with the use of SF and YE560, as reflected in responses on the Surgeon Survey. Specifically, we hypothesize that greater than 75% of surgeons would choose to use SF and YE560 at least in the majority of future VS, meningioma, HNP, or HNS resections based on responses from the Surgeon Survey. Secondarily, we hypothesize that surgeons will rate the correlation of fluorescence with visual assessment with white light microscopy and electrostimulation to be “good” or “excellent” for over 75% of the cases.
15. Because the yellow fluorescence is primarily comprised of red and green components, we hypothesize that RGB component analysis of intraoperative images will yield significantly higher red and green values in the VS compared to the facial and cochlear nerves. Similar analysis may be conducted between the tumor and surround nerves or structures of interest for meningiomas, HNP, and HNS.

3.5. Design and Proposed Analysis

16. The feasibility study will involve 90 patients, focusing on intra-operative visualization of fluorescein using YE560 in VS, meningioma, HNP, or HNS, inclusive of recurrent tumors, previously radiated tumors, and patients with neurofibromatosis type 2. There will be an allowance to enroll up to 95 patients to meet the goal of 90 subjects if subjects are withdrawn from the study due to a different pathologic entity diagnosed on biopsy of the tumor. Establishing the optimal dose and timing for FS will be a part of the feasibility study. Flexibility will be allowed with the dose and timing to achieve optimal visualization condition based on surgeon feedback with a maximum cumulative dose of 500 mg (standard dosage for ophthalmology angiography). The study will be largely descriptive, documenting the macroscopic appearance of FS and describing surgeon observations with regards to timing of peak fluorescence, correlation with electrostimulation, and utility in differentiating normal tissue from tumor.
17. Images containing the tumor and facial and cochlear nerves (or other relevant structures of interest in the case of meningioma, HNP, or HNS) will be captured with the microscope with the YE560 filter by the surgeon and analyzed; the YE560 filter will then be turned off and another identical image will be captured under white light microscopy for the separate survey validation analysis. For the RGB component image analysis, the fluorescence of the tumor will be measured in comparison to the facial nerve and cochlear nerve using ImageJ image analysis software to quantify the red, green, and blue components of the images. Inferential statistics will be used to compare the red, green, and blue components of regions of interest from the VS and the adjacent facial or cochlear nerve.
18. For the survey validation analysis, we will validate the question “How well did fluorescence correlate with your visual assessment of the tumor and nerve tissue under normal microscopy without the Yellow 560 filter?” The neurosurgeons and neurologists will be presented with 30-60 second videos of the VS and facial and/or cochlear nerves, with and without YE560 active. The surgeons will respond to the above question with choices of “no correlation,” “some

correlation,” “good correlation,” and “excellent correlation.” Other questions from the surgeon survey will not be validated due to the scope of the feasibility study.

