3.6.9. Secondary Endpoints

The first secondary endpoint is the differential measurement of red, green, and blue levels in VS tissue compared to the facial nerve and cochlear nerve using FS and YE560. ImageJ software will be used to analyze representative images capture from microsurgery. The operating surgeon will delineate regions of interest for the VS, facial nerve, and cochlear nerve. Separate similar analysis will be performed for other tumor types.

The second secondary endpoint will include gross total resection rate, postoperative facial nerve function, and postoperative hearing status. Facial nerve function will be assessed by clinical evaluation at 3 month postoperative visits as well as intraoperative supramaximal stimulation and minimum stimulation levels as routinely performed in surgery.

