3.6.11. Microscope imaging during YE560 fluorescence use

1. Standard methods of anesthesia as appropriate for open craniotomy or otologic surgery will be used.
2. Surgeons will gain access to the lesion of interest through a craniotomy or translabyrinthine approach.

3. At the time of tumor exposure, patients will be given intravenous FS. The timing and dose may vary. Maximum cumulative dose will not exceed 500 mg.

- Initial dosing protocol will be 1 mg/kg intravenous FS.
 - If insufficient fluorescence is obtained or washout occurs, additional doses of 1 mg/kg may be administered
- Based on the experience of the first 3 cases, modifications to the dosing protocol may be made.
 - A higher, single dose may be administered if there is insufficient fluorescence or premature washout. Additional doses may be given during surgery.
 - If saturation of normal tissue with fluorescence occurs, the dose may be decreased or the FS may be administered at an earlier time point (opening of dura, anesthesia induction, etc.) during subsequent cases
- Continued adjustments may be made to the dosing and timing, with a goal of standardizing the dose after 10 cases

4. Once the VS has been surgically exposed and FS has been administered, the YE560 fluorescence module shall be used to visualize fluorescence in the tissue. Images will be captured prior to tumor dissection, after exposure of the intracapsular tumor contents, and after maximum resection. A pair of images—one using the YE560 and one with white light microscopy—will be captured during each event.

5. With the YE560 turned on, images will be captured with the microscope. Video recording from the Pentero 900 and Kinevo 900 microscopes will be captured for the entirety of their use in the case.

6. The time from injection until to the point where the differential fluorescence is greatest will be recorded and documented in the surgeon's survey. Circulating nursing staff will record timestamps in collaboration with instruction from the operating surgeons.

7. The YE560 module will be applied during the aforementioned events and additionally at the discretion of the operating surgeons. Depending upon the number of potential regions identified for imaging and for possible biopsies, the YE560 fluorescence module is expected to add less than 10 minutes to the overall procedure.

8. At any time, the operating surgeon may turn off the YE560 module as dictated by the needs of surgery.

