4.5. Summary of Device Design

The Instruction for use covers basic set-up and use of the KINEVO 900 equipped with YE560 fluorescence option

The YE560 option is an accessory for intra- operative illumination of the surgical field with light of a wavelength between 460nm and 690nm.

The integrated fluorescence module YE560 serves to make fluorescent areas visible. It is designed for stimulus light penetrating the service in a wave length range from 460nm to 500nm and for visualizing the YE560 fluorescence light reflected by the service in a wave length range of 540nm to 690nm.

Surgeons can switch between white light and fluorescence mode. Blue excitation light should be dimmed for optimum reproduction of the fluorescence light.

The YE560 lighting option can be operated from the hand grip or foot switch. The user manual explains how to set-up, operate and record images taken with the YE560 module.

5. Training and Experience Requirements for use of the Device

The Instruction for use covers basic set-up and use of the YE560 fluorescence option as well as recording function for capturing pictures. Training in the use of YE560 for all operating surgeons in this study will be provided by the Sponsor representative before use in surgery on enrolled subjects. A training log documenting personnel and training dates will be kept by the study coordinator. All study cases will be assisted by a sponsor representative.

[figure not shown]
6. Description of Medical/Surgical Procedures involved in the use of the device

The YE560 fluorescence option will be used during open craniotomy procedures performed for the purpose of tumor resection and possible biopsy. Standard neurosurgical techniques shall be used throughout the procedure. The YE560 fluorescence will be used during the surgery, once the tumor is exposed. The YE560 fluorescence visualization option can be turned on/off during the tumor resection phase of the surgery. Images captured with the KINEVO 900 under YE560 light and simultaneously navigation pictures, representing the location of the biopsy during surgery will be linked to the biopsy results available after surgery. To obtain images, a fluorescent contrast agent is required. Fluorescein Sodium will be administered intravenously prior to imaging within its labelled dose range for its approved use in ophthalmic applications to reveal fluorescence contrast during the use of YE560.

7. Study Drug

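### The RGB endpoint measures tumour-nerve contrast on post-dye YE560 images only, so it cannot show a gain over white light, although the paired white-light images needed are already captured

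*Protocol*

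**What the plan says.** Protocol 3.4 (item 15) gives the reasoning, "Because the yellow fluorescence is primarily comprised of red and green components", and then the prediction: "RGB component analysis of intraoperative images will yield significantly higher red and green values in the VS compared to the facial and cochlear nerves". Protocol 3.5 (item 17) says that images containing tumour and nerves "will be captured with the microscope with the YE560 filter by the surgeon and analyzed". The filter is then switched off and "another identical image will be captured under white light microscopy for the separate survey validation analysis". The same item describes the analysis, in a sentence that closes by naming the cochlear nerve as the alternative: "Inferential statistics will be used to compare the red, green, and blue components of regions of interest from the VS and the adjacent facial or".

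Protocol 3.6.9 defines the first secondary endpoint as the tumour-nerve difference in RGB levels with fluorescein and YE560. It says "ImageJ software will be used to analyze representative images capture from microsurgery", and the operating surgeon draws the regions. Protocol 3.6.11 (item 4) fixes three capture events, all after fluorescein has been given: "Images will be captured prior to tumor dissection, after exposure of the intracapsular tumor contents, and after maximum resection". Each event yields one YE560 and one white-light image.

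**The concern.** Nerve serves as a control tissue, but the endpoint has no control condition. Tumour and nerve may differ in red and green because of their own colour, surface or lighting, with or without the dye. A significant difference on YE560 images would therefore not show how much of it is fluorescence, or whether a surgeon would see as much under white light. Both questions matter to how the result will be read: section 3.4 explains the expected difference by fluorescence, and section 1.3 hypothesises that the aid helps the surgeon tell tumour from nerve more clearly.

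The choice of image is a second, smaller matter. The three events fall at different times after injection, and the Protocol does not say which event's image counts as representative. The contrast reported may depend on that choice.

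**Working it through.** **1. What each question needs, and what is planned.**

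| Question | Comparison needed | In the RGB endpoint? | Images planned? |
|---|---|---|---|
| Do tumour and nerve differ under fluorescein plus YE560? | Tumour against nerve, YE560, post-dye | Yes | Yes |
| Does YE560 show more contrast than white light? | The same contrast on the paired white-light image | No | Yes, at each of three events (3.6.11 item 4) |
| Is the difference due to fluorescein? | The same contrast under YE560 before injection | No | No |

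The second row can be filled from images already in the plan. Section 3.5 item 17 assigns the white-light stills to the survey validation. Item 18 and section 3.6.11 item 12 describe that validation as using edited videos, while section 3.6.8 speaks of images. Either way, measuring the stills as well takes nothing from the validation.

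**2. What the paired difference estimates.** Write the tumour-nerve contrast on a YE560 image as C_Y = I_Y + F, where I_Y is the intrinsic contrast through the filter and F is the dye's contribution. On the white-light image, C_W = I_W + G, where G is whatever the dye adds under white light. Then

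C_Y − C_W = (F − G) + (I_Y − I_W).

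This is the gain of YE560 over white light. It equals the dye effect F only if I_Y = I_W and G = 0, and the documents establish neither.

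**3. Illustration of size.** The Protocol states no alpha, SD, effect size or power for this endpoint, so there is no figure to reproduce. Everything here is assumed: a paired two-sided 5% test, one image pair per patient, zero dye effect, an intrinsic contrast of d SDs of the paired tumour-nerve difference, and 30, 60 or 90 patients. The Protocol gives 90 over all tumour types and no number for vestibular schwannoma.

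Test on YE560 images alone: P(significant) = Φ(d√n − 1.96) + Φ(−d√n − 1.96).

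- d = 0.3, n = 90: d√n = 0.3 × 9.487 = 2.846; Φ(0.886) = 0.81.
- d = 0.3, n = 60: 0.3 × 7.746 = 2.324; Φ(0.364) = 0.64.
- d = 0.3, n = 30: 0.3 × 5.477 = 1.643; Φ(−0.317) = 0.38.
- d = 0.5: 0.78 (n = 30), 0.97 (n = 60), 0.997 (n = 90).

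Test of the within-pair change, where the control image has the same intrinsic contrast and the within-patient correlation is 0.5 (10,000 simulated studies per setting): significant in 4.5% to 5.4%.

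Change in contrast detectable with 80% power: (1.960 + 0.842)/√n = 0.30 SD (n = 90), 0.36 (n = 60), 0.51 (n = 30), in SDs of the within-pair change.

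The formula depends only on the size of d. If the intrinsic difference favoured nerve, the same percentages would apply to a result against the hypothesis.

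**4. Optics.** Section 4.5 first describes "illumination of the surgical field with light of a wavelength between 460nm and 690nm", which covers the whole 540-690 nm viewing band. Its next paragraph gives stimulus light of 460-500 nm, which ends 40 nm below that band (540 − 500). The second description makes a dye origin plausible. Neither replaces a measurement of undyed tissue.

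**5. Timing.** Section 3.4 suspects a peak at a time similar to the 20-30 minutes reported for gliomas, and section 3.6.11 allows for washout and repeat doses. The Appendix 3 survey records the times of dosing, peak, saturation and loss of useful fluorescence, but not of each image. Nursing timestamps and continuous video (3.6.11 items 5 and 6) should allow image times to be recovered.

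**The case against.** The strongest reply is that the endpoint asks a narrower question and answers it. The objective in section 3.1 is to quantify how far fluorescent tumour and adjacent nerves can be told apart by RGB analysis. A tumour-nerve comparison under fluorescein plus YE560 does that. Benefit is judged by the surgeon survey, which has its own question on agreement with white light. The study is a largely descriptive feasibility study, and this endpoint is secondary. All of that stands, so a reader who inferred that the endpoint fails its objective would go too far.

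Four other strong readings are not supported:

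- **Reflected light contaminates the signal.** The wider illumination range in section 4.5 invites this, but the 460-500 nm stimulus range in the same section does not overlap the viewing band.
- **The result is biased upward.** The documents give neither the sign nor the size of any intrinsic colour difference.
- **The highest-contrast image will be picked.** Representative does not mean maximal, so an inflation computed for taking the best of three events has no basis in the text. A detailed selection rule could also stand in a statistical analysis plan that is not shown.
- **The white-light image is a no-dye control.** It is taken after injection, so it is not.

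It is also fair to say that the percentages above show only that a test finds a difference one has assumed. They illustrate the ambiguity and do not estimate its size in this trial.

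What remains is that section 3.4 credits the difference to fluorescence, section 1.3 hopes for clearer distinction, and the endpoint as defined can establish neither.

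**Conclusion.** The point holds as a cheap improvement. The RGB endpoint describes tumour-nerve contrast under fluorescein plus YE560. It cannot show that this contrast exceeds white-light contrast, and it cannot by itself separate fluorescein signal from intrinsic colour. Leaving the images to be chosen as representative also leaves the event, and so the time since injection, open.

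The size in this trial is unknown because the Protocol gives no intrinsic contrast. On the assumed values, a significant result with no dye effect ranges from 38% (0.3 SD, 30 patients) to 99.7% (0.5 SD, 90 patients), against about 5% for the paired test. That 5% requires the intrinsic contrast to be equal in the two images. For a white-light partner, it is the error rate under no gain over white light, not under no dye uptake.

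**What to change.** In Protocol 3.5 item 17 and 3.6.9:

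- Measure the same tumour and nerve regions on the white-light image paired with each YE560 image.
- Report the within-pair change in a normalised tumour-to-nerve red and green contrast, such as a ratio, beside the raw YE560 difference. Raw RGB values are not on the same scale in the two modes, so keep camera settings fixed.
- Replace representative images with all protocol-event pairs in which both tissues are visible, and allow for repeated pairs per patient (for example a patient random effect, or one mean per patient).
- Report contrast against time since the latest dose, taken from the timestamps and video.
- State that the paired result addresses the gain of YE560 over white light. Draw no conclusion on dye uptake unless a pre-injection YE560 image of the same field happens to be available.

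The cost is further ImageJ work on images already captured: at most 90 × 3 = 270 pairs, and fewer where tumour and nerve are not both in view. The reported contrast will probably look less favourable than the raw YE560 difference. No dose, injection time or surgical step changes.
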